## ABBREVIATIONS AND DEFINITIONS OF TERMS

AE	Adverse Event
Category B Drug	Animal reproduction studies have failed to demonstrate a risk to the fetus and there are no adequate and well-controlled studies in pregnant women
CEUS	Contrast-Enhanced Ultrasound
CFR	Code of Federal Regulations
CHOP	Children's Hospital of Philadelphia
CT	Computed Tomography
DSMP	Data Safety Monitoring Plan
FDA	Food and Drug Administration
HIPAA	Health Insurance Portability and Accountability Act
ICU	Intensive Care Unit
IDS	CHOP Investigational Drug Service
IND	Investigational New Drug
IV	Intravenous
IRB	Institutional Review Board
Lumason™	FDA-approved for contrast-enhanced ultrasound; the investigational drug
MRI	Magnetic Resonance Imaging
NEC	Necrotizing Enterocolitis
ORC	The CHOP Office of Research Compliance
PI	Principal Investigator
Pneumatosis intestinalis	Gas cysts in the intestinal wall, sometimes indicative of necrotizing enterocolitis
PHI	Protected Health Information
SAE	Serious Adverse Event
US	Conventional Ultrasound Scan
XR	Abdominal Radiography
PACS	Picture Archiving and Communication System

## ABSTRACT

### Context:

There is no bedside imaging technique that can quantify dynamic bowel perfusion with high soft tissue contrast and sensitivity. Our goal is to assess the feasibility of utilizing contrast-enhanced ultrasound (CEUS) in bedside monitoring of bowel perfusion in neonatal necrotizing enterocolitis.

### Objectives:

- Primary: Assess bowel perfusion characteristics in necrotizing enterocolitis using CEUS.
- Secondary: Optimize the CEUS scanning technique and quantification methods for clinical translation.

### Study Design:

Single site, open-label clinical study.

### Setting/Participants:

Subjects in the neonatal or pediatric intensive care unit aged 1.5 years or younger with suspected or diagnosed necrotizing enterocolitis.

The study will be performed at Children's Hospital of Philadelphia (CHOP). CHOP will be the only site of the study.

### Study Interventions and Measures:

Contrast-enhanced ultrasound scan with a duration of approximately 20 minutes. Qualitative analysis with visual assessment and quantitative analysis of the acquired scans will be performed by the sponsor-investigator. The scans will be assessed for diagnostic quality of images, artifacts encountered, and the presence of additional contributory diagnostic information.

## PROTOCOL SYNOPSIS

---

Study Title	Evaluation of Bowel Perfusion with Contrast-Enhanced Ultrasound in Necrotizing Enterocolitis
Funder	Children's Hospital of Philadelphia
Clinical Phase	Phase II
Study Rationale	
Necrotizing enterocolitis (NEC) is a devastating disease of the newborn affecting 1-5% of all neonatal Intensive care unit (NICU) admissions and up to 10% of neonates under 1500 g with mortality rates of 50% or higher depending on severity [1]. Bowel wall perforation occurs in 12%-31% of patients with NEC, increasing the mortality rate from 30% to 64% [2]. Therefore, early detection of ischemia and necrotic bowel which leads to perforation is vital in improving morbidity and mortality associated with NEC. Abdominal radiography, the standard imaging algorithm for monitoring of NEC, has a low sensitivity of 40% in the diagnosis of severe NEC with necrotic bowel [1].
 
Currently, there is no bedside tool with high soft tissue contrast to accurately monitor and quantify bowel perfusion in pediatric patients. Bowel perfusion is altered in developing ischemia which is important for early diagnosis and intervention in neonatal necrotizing enterocolitis, a disease of high mortality and morbidity if diagnosed late. Note that the current standard algorithm for diagnosis of necrotizing enterocolitis is abdominal radiography, which misses up to 60% of advanced necrotizing enterocolitis. If the disease is missed at an early stage, highly morbid surgeries consist of extensive surgical resection of bowel which are not without serious potential complications. Abdominal ultrasound can be obtained to assess for gross complications of advanced necrotizing enterocolitis such as pneumatosis intestinalis or complex ascites but its diagnostic sensitivity for early necrotizing enterocolitis is limited. As compared to CEUS, color Doppler quantification of bowel perfusion offers suboptimal soft tissue contrast and inaccuracies related to artifact. As compared to CEUS, MRI is not easily obtainable in neonates and infants due to cost, support staff, transport and/or sedation requirements. CEUS on the other hand permits serial monitoring of bowel perfusion at the bedside with high soft tissue contrast and at lower cost than MRI. Further validation of this technique and standardization of

---

---

quantification methods will prove to be of significant clinical value

There is a dire need to introduce better imaging tools such as contrast-enhanced ultrasound to the clinical setting that can detect NEC at an early stage and prompt therapeutic implementation. In this regard, contrast-enhanced ultrasound (CEUS) enables safe, serial monitoring of dynamic quantification of bowel perfusion at the bedside.

Safety of intravenous use of Sulfur hexafluoride lipid-type A microspheres was based on evaluation of published literature involving use of Lumason™ in over 900 pediatric patients, as noted on the 2016 FDA product label. Non-fatal anaphylaxis was reported in one pediatric patient, but none in a neonate. Animal data of daily intravenous administration of Sulfur hexafluoride lipid-type A microspheres to rats (administered up to 10 times the recommended maximum human dose) and rabbits (administered up to 20 times the recommended maximum human dose) for 30 consecutive days and 14 consecutive days, respectively, resulted in no toxicity to the fetus in animal studies, as noted on the 2016 FDA product label. Specifically pertaining to the use of Sulfur hexafluoride lipid-type A microspheres in bowel imaging in pediatric patients, we expect a similar risk of adverse events. For the proposed study, the same pediatric dosage, route of administration, safety monitoring guidelines, and low mechanical index used for contrast ultrasound settings will be used.

---

Study Objective(s)	
Primary
 

Assess bowel perfusion characteristics in necrotizing enterocolitis using CEUS.

 
Secondary
 

Optimize the CEUS scanning technique and quantification methods for clinical translation.

Test Article(s)	Sulfur hexafluoride lipid-type A microspheres (Lumason™, Bracco Inc) is an FDA-approved ultrasound contrast agent which consists of active ingredients including Sulfur hexafluoride (strength 60.7 mg in 1 mg), Distearoylphosphatidylcholine, DL- (strength 0.19 mg in 1 mg), 1,2-Dipalmitoyl-Sn-Glycero-3-Phospho-(1'-Rac-

---

---

Glycerol), Sodium Salt (0.19 mg in 1 mg). Inactive ingredients include Polyethylene Glycol 4000 (strength 24.56 mg in 1 mg) and Palmitic Acid (0.04 mg in 1 mg). The Sulfur hexafluoride lipid microspheres are composed of SF6 (molecular weight 145.9) gas in the core surrounded by an outer shell monolayer of phospholipids consisting of 1,2-Distearoyl-sn-glycero-3-phosphocholine (DSPC) and 1,2-Dipalmitoyl-sn-glycero-3-phosphoglycerol, sodium salt (DPPG-Na) with palmitic acid as stabilizer. Sulfur hexafluoride lipid-type A microspheres fall under Category B, that is, animal reproduction studies have failed to demonstrate a risk to the fetus and there are no adequate and well-controlled studies in pregnant women. 1,2-Distearoyl-sn-glycero-3-phosphocholine (DSPC), with empirical formula C44H88NO8P, has a molecular weight of 790.6. 1,2-Dipalmitoyl-sn-glycero-3-phospho-rac-glycerol sodium (DPPG-Na), with empirical formula C38H74 NaO10P, has a molecular weight of 745.

---

Study Design	Single site, open-label clinical study.
Subject Population	Inclusion Criteria
key criteria for Inclusion and Exclusion:	
 
1. Males and females aged 1.5 years or younger
 
2. Post menstrual age of 29 weeks or older
 
3. Patients with suspected or diagnosed necrotizing enterocolitis
 
4. Patient in the CHOP NICU or PICU
 
5. Parental permission
 

	Exclusion Criteria
	
 
1. Medical history of Lumason hypersensitivity
 
2. Hemodynamic instability as defined by rapid escalation of cardiopulmonary support in the past 12-24 hours, as defined by the clinical care team including <math>\geq 1</math> intensive care physician not part of the study team
 

---

---

3. Pulmonary insufficiency as defined by FiO2 requirements of >40% and/or subjects with pulmonary hypertension requiring nitric oxide

---

**Number Of Subjects** 200; CHOP will be the only site of the study.

---

**Study Duration** The study duration per subject will be approximately 20 minutes including the time to prepare Lumason™ contrast agent and perform the pre-contrast imaging and the CEUS, as well as the 60 minute monitoring period after the first and second injection of Lumason™. A second CEUS may be performed at the time of suspected or diagnosed NEC, and at the time of surgery (for subjects undergoing surgery as part of clinical care) or at short-term follow-up of clinical condition (approximately within 1-2 weeks from the first scan) for a total of two CEUS exams of 1 hour and 15-minute duration each.

Study participation will be complete when the 60-minute monitoring period after the last CEUS performed is complete (after the first CEUS in patients who undergo one exam, or after the second CEUS is complete in patients who undergo two exams).

**Study Treatment** CEUS has a total duration of 1 hour and 20 minutes: CEUS has a duration of approximately 20 minutes for the CEUS and 60 minutes for post-examination monitoring of potential adverse events.

---

**Efficacy Evaluations** There are no efficacy evaluations for this diagnostic study. The endpoints of this study are:

**Primary Endpoint**

- The primary objective of this study is to evaluate whether CEUS technique can be utilized to detect early alterations in bowel perfusion in NEC. The differences in bowel perfusion between normal subjects (those with suspected or at risk of necrotizing enterocolitis but turn out to be normal on imaging and clinical evaluation) versus NEC patients will be assessed qualitatively and quantitatively using the CEUS technique, as detailed above.

---

---

Secondary Endpoint	

 
Diagnostic quality of the CEUS exams will be evaluated with the scoring system of non-diagnostic (1), moderate artifacts degrading diagnostic quality (2), mild artifacts without degradation of diagnostic quality (3), and diagnostic (4).
 
	
Pharmacokinetic Evaluations	There are no pharmacokinetic evaluations.
Safety Evaluations	All subjects entered into the study and receiving at least one injection of investigational drug will be included in the safety analysis. The frequencies of AEs by type, severity, and temporal relationship to the CEUS scan will be summarized. SAEs (if any) will be described in detail.
Statistical And Analytic Plan	Baseline and demographic characteristics will be summarized by standard descriptive summaries. All subjects entered into the study and receiving at least one injection of investigational drug will be included in the safety analysis. The frequencies of AEs by type, severity, and temporal relationship to the CEUS scan will be summarized. SAEs (if any) will be described in detail. Details of sample size and power calculations for this study are described in Section 6 of the protocol.
DATA AND SAFETY MONITORING PLAN	The safety monitoring for this study is the primary responsibility of the sponsor-investigator. Monitoring the safety outcomes following IV administration of the investigational drug will be conducted primarily by the Principal Investigator and/or specifically designated study personnel. An independent safety monitor will be designated to oversee the safety reports, and help adjudicate attribution of serious adverse events, should they occur. Regular meetings to discuss the outcomes of the study, and of the safety events, will be conducted by the study team. The occurrence of adverse events, serious adverse events and unanticipated events will be reported by the study team in accordance with federal and institutional guidelines, as outlined in Section 8 of this clinical study.

Prior to study initiation, the Office of Research Compliance (ORC) will conduct a pre-trial monitoring visit, to assess trial readiness of the study staff. Once the pre-trial monitoring visit has been successfully completed, the ORC will also monitor the IND study on at least an annual basis.
	

---

## 1 Background Information and Rationale

### 1.1 Introduction

Necrotizing enterocolitis (NEC) is a devastating disease of the newborn affecting 1-5% of all neonatal Intensive care unit (NICU) admissions [1] and up to 10% of neonates under 1500 g. Bowel wall perforation occurs in 12%-31% of patients with NEC, increasing mortality rate from 30% to 64% [2]. Therefore, early detection of ischemia and necrotic bowel which leads to perforation is vital in improving morbidity and mortality associated with NEC. Despite extensive research and improvements in the field of neonatal care, the morbidity and mortality associated with NEC have remained unchanged over the last 3 decades [3]. Strategies and sensitive/specific tests for predicting and preventing NEC are lacking.

Contrast enhanced ultrasound (CEUS) is a novel technique in pediatrics which has proven itself as a safe and effective modality with benefits over conventional ultrasound (US) by its improved real-time evaluation of the micro- and macro-vascularity of normally and abnormally perfused tissue [4]. CEUS does not depend on ionizing radiation, can be performed bedside and the ultrasound contrast agent used is not associated with renal toxicity. There have been no studies on the use of CEUS to evaluate NEC. Despite the favorable safety profile and diagnostic benefits, the paucity of CEUS studies for NEC in the U.S. resulted from the off-label usage of this novel contrast agent.

Abdominal radiography (XR) and computed tomography (CT) have been the diagnostic gold standard for NEC but are far from flawless [5, 6]. Pneumoperitoneum is the only radiologic sign that has been universally agreed upon as an indication for surgical intervention (i.e. laparotomy or peritoneal drainage) for patients with NEC, however not all neonates with bowel necrosis and perforation have free air on XR [1, 7]. Bowel dilation is a nonspecific finding in NEC that remains best appreciated on XR and is sometimes the only sign present in NEC [8]. Additional findings suggestive of NEC on XR include intramural air and portal venous air. Abdominal XR remains a necessary, primary imaging modality for the evaluation of NEC. However, signs of NEC on XR may be subtle, can easily be missed, especially in the early stages of NEC and consequently provide limited information that could lead to clinical interventions that may prevent or predict the onset of NEC [6].

Conventional abdominal ultrasound (US) has been implemented as a useful adjunct to XR for the early detection of intramural air, bowel wall edema, decreased peristalsis, and decreased or absent perfusion that suggests bowel wall ischemia/necrosis. Furthermore, hyperechogenic air bubbles may be seen within the diseased bowel wall. US may show pathology before XR becomes abnormal. Near-infrared spectroscopy (NIRS) is another non-invasive technique that has shown promise in improving early detection of NEC but suffers from limited depth penetration and poor soft tissue contrast [6]. CT and magnetic resonance imaging (MRI) have a very limited role in the diagnostic work up of NEC because the critically sick children have to be transported to either the CT or MRI suite. Furthermore, CT uses ionizing radiation which should be avoided

when possible in these very young, radiation sensitive neonates and MRI studies suffer from the longer acquisition times and image degradation due to the susceptibility artifacts from the air inclusions and motion. The use of contrast enhanced ultrasound is an exciting new modality that shows promise in early and reliable prediction of NEC. These imaging modalities all leave something to be desired when it comes to the evaluation, prediction and prevention of NEC.

In summary, the current imaging algorithm is not sensitive enough to detect early NEC and prevent high mortality and morbidity associated with the disease. There is therefore a dire need to introduce better imaging tools to the clinical setting that can detect NEC at early stage and prompt therapeutic implementation.

## **1.2 Name and Description of Investigational Product or Intervention**

Sulfur hexafluoride lipid-type A microspheres (Lumason™, Bracco Inc) is FDA-approved ultrasound contrast agent which consist of active ingredients including Sulfur hexafluoride (strength 60.7 mg in 1 mg), Distearoylphosphatidylcholine, DL- (strength 0.19 mg in 1 mg), 1,2-Dipalmitoyl-Sn-Glycero-3-Phospho-(1'-Rac-Glycerol), Sodium Salt (0.19 mg in 1 mg). Inactive ingredients include Polyethylene Glycol 4000 (strength 24.56 mg in 1 mg) and Palmitic Acid (0.04 mg in 1 mg). The sulfur hexafluoride lipid microspheres are composed of SF6 (molecular weight 145.9) gas in the core surrounded by an outer shell monolayer of phospholipids consisting of 1,2-Distearoyl-sn-glycero-3-phosphocholine (DSPC) and 1,2-Dipalmitoyl-sn-glycero-3-phosphoglycerol, sodium salt (DPPG-Na) with palmitic acid as stabilizer. Sulfur hexafluoride lipid-type A microspheres fall under Category B, that is, animal reproduction studies have failed to demonstrate a risk to the fetus and there are no adequate and well-controlled studies in pregnant women. 1,2-Distearoyl-sn-glycero-3-phosphocholine (DSPC), with empirical formula C44H88NO8P, has a molecular weight of 790.6. 1,2-Dipalmitoyl-sn-glycero-3-phospho-rac-glycerol sodium (DPPG-Na), with empirical formula C38H74 NaO10P, has a molecular weight of 745. In pediatric patients, after reconstitution 0.03 mL per kg is administered intravenously. The weight-based dose of 0.03 mL per kg will be repeated twice during a single examination. Following each injection, an intravenous flush of 0.9% Sodium Chloride is injected.

## **1.3 Compliance Statement**

This study will be conducted in full accordance of all applicable Children's Hospital of Philadelphia Research Policies and Procedures and all applicable federal and state laws and regulations including 45 CFR 46. All episodes of noncompliance will be documented. Research will also be conducted in full accordance with Food and Drug Administration (FDA) regulations 21 CFR 50 (Protection of Human Subjects), 21 CFR 56 (Institutional Review Boards) and 21 CFR 312 (Investigational New Drug).

The investigators will perform the study in accordance with this protocol, will obtain consent, and will report unanticipated problems involving risks to subjects or others in accordance with The Children's Hospital of Philadelphia IRB Policies and Procedures and all federal requirements. Collection, recording, and reporting of data will be

accurate and will ensure the privacy, health, and welfare of research subjects during and after the study.

## **2 STUDY OBJECTIVES**

The purpose of the study is to evaluate bowel perfusion in neonatal necrotizing enterocolitis using the CEUS technique and optimize the technique for clinical use.

### **2.1 Primary Objective (or Aim)**

The primary objective of this study is to evaluate the altered bowel perfusion in neonatal necrotizing enterocolitis using the CEUS technique.

### **2.2 Secondary Objective (or Aim)**

The secondary objective is to optimize and standardize the CEUS scanning technique and quantification method.

## **3 INVESTIGATIONAL PLAN**

### **3.1 General Schema of Study Design**

Patients with suspected or diagnosed necrotizing enterocolitis will be recruited for the study. Following parental consent, the subject will undergo an investigational CEUS exam, which will be performed separately from any clinically indicated conventional ultrasound. CEUS duration of approximately 20 minutes, followed by 60 minutes of monitoring. A second CEUS may be performed at the time of surgery (for subjects undergoing surgery as part of clinical care) or at short-term follow-up of clinical condition (approximately within 1-2 weeks from the first scan) for a total of two CEUS exams of 1 hour and 20-minute duration each. The CEUS exam includes a pre-contrast ultrasound evaluation with FDA-approved technologies (e.g. gray-scale ultrasound, Doppler ultrasound, microvascular imaging).

#### **3.1.1 Screening Phase**

Potential subjects will be identified by: 1) Identification by neonatologists of patients requiring abdominal ultrasound during the neonatal or pediatric intensive care unit stay for suspected, at risk of or diagnosed necrotizing enterocolitis.

Before discussing participation in the study, we will confirm eligibility by reviewing the subjects' medical records. Participation will be discussed between the PI and the referring neonatologist. Participation will be discussed with the parents/guardian by the neonatologist and/or radiologist after identification and confirmation of eligibility. Consent of the parents/guardian will be obtained prior to the exam by the PI, co-investigator, or neonatologist co-investigator in a private setting. Questions will be answered by the PI, co-investigator, or referring neonatologist co-investigator.

### **3.1.2 Study Treatment Phase**

Investigational CEUS scan will be performed separately from any clinically indicated conventional US, in the ICU. A second CEUS may be performed at the time of suspected or diagnosed NEC, and at the time of surgery (for subjects undergoing surgery as part of clinical care) or at short-term follow-up of clinical condition (approximately within 1-2 weeks from the first scan) for a total of two CEUS exams of 1 hour and 20-minute duration each. Injection of Lumason™ contrast agent will be performed via the existing peripheral intravenous line or central line using the FDA-recommended dose of up to 0.03 mg/kg. Contrast-agent injection will be performed twice per CEUS scan to ensure image quality and test reproducibility. In the case of more stable patients without an IV line, a peripheral IV line will be started to conduct the investigational CEUS. Two bolus injections will be performed to evaluate for dynamic bowel perfusion and several 2-minute cine clips as well as static images will be acquired during the exam.

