## 7 STUDY DRUG

### 7.1 Description

Lumason™ is currently FDA approved for use in the pediatric population for echocardiography and evaluation of focal hepatic lesions, and very recently (Jan 2017) approved for use in children for the evaluation of the urinary tract in pediatric patients with known or suspected vesicoureteral reflux. Previously, the presence of cardiac shunts was a contraindication for its use, but this was recently cancelled by the FDA as of December 2016. However, for this clinical study, the FDA has recommended that subjects with hemodynamically significant PDA and right-to-left cardiac shunts be excluded from study participation. Ultrasound contrast agents have been approved for use in Europe for almost two decades. In the case of SonoVue (now called Lumason™), a second-generation lipid/sulfur hexafluoride US contrast agent (Bracco, Milan, Italy), the European Union approved its intravenous use in adults in 2001. The FDA in the United States just recently approved the use of Lumason™ for evaluation of focal hepatic lesions in the pediatric population in 2016. Through decades of clinical utilization of ultrasound contrast agents, there are established recommended doses for the intravenous route of administration. Recommended intravenous dose for Lumason™ is weight-based, 0.03mL/kg as an intravenous injection. As an example, for the intended study population it may be roughly estimated that the maximum weight of an infant 1 year of age may be up to approximately 10 kg, for a maximum dose of 0.30 mL. Two injections per exam will be performed.

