### 7.2 Dosing

Through decades of clinical utilization of ultrasound contrast agents, there are established recommended doses for the intravenous route of administration. Recommended intravenous dose for Lumason™ is weight-based, 0.03mL/kg as an intravenous injection, up to a maximum of 2.4mL per injection. As an example, for the intended study population it may be roughly estimated that the maximum weight of an infant 1 year of age may be up to approximately 10 kg, for a maximum dose of 0.30 mL. Two injections per exam will be performed. Since investigational findings are subject to pre-analytic variability, performing two contrast-agent injections facilitates validation of findings if reproducibility is found. No increased risk was found at initial experience at Johns Hopkins Hospital, where 5 of 10 patients required double injection of contrast-agent. Clinical cases at Johns Hopkins Hospital and The Children's Hospital of Philadelphia have required double injection due to variable factors such as microbubble trapping within intravenous tubing. Adverse effects are not dose-dependent, thus risk is not increased by modifying the timing of interventions or increasing the number of contrast-agent injections.

Even though the initial dosing of investigational drug for this study is 0.03 mL/kg, it is possible that the optimal dose for CEUS imaging of hypoxic ischemic injury may be less than 0.03 mL/kg. Since there would be no apparent safety concern regarding the administration of a lower dose of the investigational drug, the study team would proceed with a lower dose administration, if initial imaging studies suggest that a dose less than

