0.03 mL/kg may provide more optimal imaging results. Therefore, the study team proposes that a dose range of 0.01-0.03 mL/kg be considered for dose optimization of the initial subjects, as indicated. Based on the published report of safe infusion of the investigational drug in four premature infants from 26.9 to 29.5 weeks gestational age [15] as well as 3 additional premature subjects from unpublished data of the sponsor, this dose range seems appropriate. For each subject, the dose per injection, as well as the total dose delivered, will be recorded in the study file for each administration of study drug. The expectation is that the intravenous injection of this ultrasound contrast agent will permit noninvasive, non-ionizing delineation of physiology and pathophysiology with higher resolution and accuracy than conventional ultrasound techniques. Since preliminary studies at Hopkins showed that half of neonates required two injections of contrast agent to achieve evaluable CEUS images, two injections will be performed per CEUS scan in all subjects to ensure adequate image quality and reproducibility.

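### Section 3.1.2 gives the injection dose in mg/kg where Sections 1.2, 7.1 and 7.2 give mL/kg; and if the lower doses in 7.2 are used, Section 6 should stratify the intensity comparison by dose

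*Combined protocol and SAP*

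**What the plan says.** **Dose unit.** Section 3.1.2, which describes how the injection is given, has the agent administered "using the FDA-recommended dose of up to 0.03 mg/kg". Section 7.2 gives the recommended dose as "weight-based, 0.03mL/kg as an intravenous injection, up to a maximum of 2.4mL per injection". Section 7.1 gives the same 0.03 mL/kg and applies it to an infant of "up to approximately 10 kg, for a maximum dose of 0.30 mL". Section 1.2 also states mL per kg.

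**Number of injections.** Section 1.2 says "The weight-based dose of 0.03 mL per kg will be repeated twice during a single examination". Sections 3.1.2, 7.1 and 7.2 specify two injections per scan.

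**Lower doses.** Section 7.2 starts at 0.03 mL/kg but says that "the optimal dose for CEUS imaging of hypoxic ischemic injury may be less than 0.03 mL/kg", that "the study team would proceed with a lower dose administration, if initial imaging studies suggest" this would image better, and proposes that "a dose range of 0.01-0.03 mL/kg be considered for dose optimization of the initial subjects". It also has the dose recorded for each injection and in total.

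**Analysis.** Section 5 derives wash-in rate, time to peak, peak intensity and area under the curve. Section 6 compares these between NEC and control infants by a Wilcoxon test and names no stratum, covariate, normalisation or exclusion for dose. Section 6.4 describes contrast ultrasound as quantifying absolute intensity.

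**The concern.** The two parts are separate and should be weighed separately.

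The first is a wrong unit in the dose statement of an intravenous drug protocol for critically ill infants. Someone working from 3.1.2 alone could not turn it into a volume. The documents give no mg-per-mL concentration, and Section 1.2 prints strengths per milligram ("active ingredients including Sulfur hexafluoride (strength 60.7 mg in 1 mg"). No statistical figure depends on this.

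The second is that a threefold dose range is allowed (0.03 / 0.01 = 3) while the outcome is on an absolute intensity scale. If intensity rises with dose, mixing doses adds variation unrelated to NEC, and the planned test loses power on peak intensity, area under the curve and wash-in rate. Time to peak and the 0-3 visual rating may be less affected.

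**Working it through.** **1. Dose check.** 0.03 mL/kg x 10 kg = 0.30 mL, which matches the example in 7.1 and 7.2. The example cannot be obtained from mg/kg without a concentration. For the wording in 1.2, two injections give 2 x 0.03 = 0.06 mL/kg per examination. A dose followed by two repeats would literally be 3 x 0.03 = 0.09 mL/kg.

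**2. The plan's own power.** Section 6.4 gives 40 per group, Cohen's d 0.71, alpha 0.05 and power 0.88. A two-sided two-sample t-test (noncentral t) gives 0.880, so the figure reproduces. The planned Wilcoxon test under normality gives about 0.865 in simulation, which is the 40/40 baseline below.

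**3. Model for mixed doses.**
- From Section 6.4: control mean 3.78, SD 1.1. NEC is lower by 0.71 x 1.1 = 0.781. These are Doppler values standing in for CEUS intensity.
- Assumed: a low-dose value is multiplied by (dose / 0.03)^g, with g = 1 (proportional) or g = 0.5 (square root).
- Assumed: low-dose infants fall at random between the groups, five, ten or twenty in total.
- Assumed: the 100 evaluable infants of Section 3.4 split 50/50, with 40/40 as in 6.4 and 30/70 as alternatives.
- Tests: unstratified Wilcoxon, and Wilcoxon stratified by dose (van Elteren), two-sided 0.05, 20,000 trials per split.

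**4. Power with the plan's mean and SD** (mean/SD = 3.78 / 1.1 = 3.4). The three unstratified values are 0.01 mL/kg with g = 1, 0.01 mL/kg with g = 0.5, and 0.02 mL/kg with g = 1.

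| NEC/control | Baseline | Low-dose infants | Unstratified | Stratified |
|---|---|---|---|---|
| 40/40 | 0.86 | 10 | 0.69 / 0.78 / 0.81 | 0.85-0.86 |
| 40/40 | 0.86 | 20 | 0.53 / 0.70 / 0.77 | 0.85-0.86 |
| 50/50 | 0.93 | 10 | 0.82 / 0.88 / 0.90 | 0.92-0.93 |
| 50/50 | 0.93 | 20 | 0.69 / 0.82 / 0.87 | 0.92-0.93 |
| 30/70 | 0.88 | 10 | 0.75 / 0.82 / 0.84 | 0.87-0.88 |

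If the first ten infants get 0.03 mL/kg and all later ones the lower dose, the 40/40 loss is the same (0.69 / 0.78 / 0.81).

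**5. Sensitivity.** At mean/SD 3.4 a threefold proportional cut moves the control mean from 3.78 to 1.26, which is 2.52 / 1.1 = 2.3 SD. That large shift drives the lowest figures. Unstratified power across the same three cases:

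| Low-dose infants | Mean/SD | 40/40 | 50/50 |
|---|---|---|---|
| 5 | 3.4 | 0.78-0.84 | 0.88-0.92 |
| 10 | 2 | 0.78-0.84 | 0.88-0.92 |
| 10 | 1.5 | 0.81-0.85 | 0.90-0.92 |

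With five infants and mean/SD 1.5, power reaches about 0.86 at 40/40 and 0.92 at 50/50, so almost nothing is lost.

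**6. Limits of stratifying.** If 0.01 and 0.02 mL/kg are pooled in one low-dose stratum, stratified power is 0.79-0.84 against 0.63-0.81 unstratified at 40/40, and 0.89-0.92 against 0.77-0.90 at 50/50. If dose has no effect, stratifying with ten low-dose infants moves power from 0.865 to 0.856 (40/40) or from 0.930 to 0.925 (50/50).

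**7. False positives.** With no true difference and random allocation of low doses, both tests reject in about 4.8-5.1% of trials.

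**The case against.** The unit error is a copy-editing matter. Section 3.1.2 calls it the FDA-recommended dose, and Section 7 states that dose with a worked volume and a cap. This stands to the extent that the intended dose is not in doubt. A reader might infer that infants will be misdosed, or that 1.2 calls for three injections. The documents do not support either inference, because every section that counts the injections says two.

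The analysis point stacks conditions. Lower doses are only to be considered, in initial subjects, if early images suggest it. The rationale names hypoxic ischemic injury rather than NEC, so the range may have been carried over from another protocol. The dose response, the number of low-dose infants and the CEUS mean/SD are all unknown. This also stands, and it is why the loss is given as a range that reaches nearly zero.

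A reader might infer that mixed doses bias the comparison. If 25% of one group and 50% of the other had low doses, and low dose shifted intensity by 1 SD, the unstratified false-positive rate at 40/40 would be about 0.14. That requires dose to be related to NEC status, and the documents give no reason to expect it.

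Other remedies exist: adjusting for recorded dose, normalising intensity, or analysing only infants at the final dose. Stratifying is the smallest change that keeps the planned rank test, but the rule must say which scan and injection set the stratum. Section 6 also justifies the sample by feasibility and protocol optimisation, which lowers the stakes of a power loss.

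**Conclusion.** The unit in 3.1.2 is wrong as written and should be corrected. The wording on repeats in 1.2 is loose and minor.

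The dose stratification is a conditional, cheap improvement. If doses are mixed and intensity depends on dose, the planned test loses power. At 40/40, unstratified power runs from about 0.53 (twenty infants at 0.01 mL/kg, proportional response, mean/SD 3.4) to about 0.86 (five infants, mean/SD 1.5). At 50/50 it runs from about 0.69 to about 0.92. With a single low dose, stratified power stays near baseline, at about 0.86 and 0.92-0.93. These figures rest on Doppler values standing in for CEUS, an assumed dose response, an assumed number of low-dose infants and random allocation. Nothing is lost if all scans use one dose. The plan's stated 0.88 is not disputed.

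**What to change.** 1. In 3.1.2, change the dose to *up to 0.03 mL/kg*.
2. In 1.2, replace the phrase about repeating the dose with *given as two injections per examination*.
3. Decide whether the 0.01-0.03 mL/kg range belongs to this study. If not, delete it from 7.2, and nothing more is needed. If so, add to Section 6: *If any subject's analysed scan uses less than 0.03 mL/kg, peak intensity, area under the curve and wash-in rate are compared by a Wilcoxon test stratified (van Elteren) by the nominal dose of the injection analysed, one scan per subject (0.03 versus below 0.03 mL/kg).*

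The cost is two wording corrections and one sentence. Dose per injection is already recorded, so no new data are needed. If every scan uses the same dose, the stratified test is the planned Wilcoxon test. If doses differ but have no effect, the price is about 0.01 of power or less.
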